3.2 Design

All enrolled heart failure subjects will be followed and assessed for outcomes for two (2) years post enrollment. The following events will be assessed at all but the baseline A visit:

- Hospitalizations
- Stroke
- Mechanical Circulatory Support Device (MCSD)*
- Transplant*
- Death (Cardiovascular related vs. Non-cardiovascular related)*

* Outcomes of death, transplant and implants of a durable VAD will be considered study endpoints with no additional follow-up in REVIVAL. When a study endpoint has been reached, events/outcomes up through the point of the outcome will be reported on the eCRFs.

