3.4 Study Visit Overview

Enrolled heart failure subjects will undergo the following Schedule for Assessments.

- 1. Clinic visits: Baseline A, Baseline B and follow up visits at 6,12,18 and 24 months. All study visits will be in person.
- 2. See Schedule of Observations and Procedures (Section 6.0) and Time and Event Schedule (Appendix A) for details regarding visit specific assessments.

3.5 **Participating Centers**

Each of the Clinical Sites and Core Laboratories selected for REVIVAL represent experienced centers in the treatment of advanced heart failure.

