4.11 Documentation of Study Events/Outcomes

Adverse events related to study procedures and outcomes will be recorded on the study eCRFs. These will be recorded using data available in the medical chart as well as information gathered on patient diaries. Diaries will be provided to all heart failure subjects at the baseline A visit to provide a convenient way for the heart failure subject to capture key details about events/outcomes. Adverse event and outcomes data will be collected at all visits following the baseline A visit and in cases of early subject termination.

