5.3 Criteria for Discontinuation or Withdrawal of a Subject

The primary reason for discontinuation or withdrawal of the heart failure subject from the study should be noted using the following categories.

- Lost to follow-up: The heart failure subject did not return to the clinic and attempts to contact the heart failure subject were unsuccessful. All attempts to contact the heart failure subject will be documented.
- Voluntary withdrawal: The heart failure subject (or heart failure subject's legally acceptable representative) wishes to withdraw from the study. The reason for withdrawal, if provided, will be recorded in the electronic case report form (eCRF).
- Study termination: The sponsor, institutional review board (IRB), ethics committee (EC), or regulatory agency terminates the study.
- Other.

The clinical investigator should document in the research record each instance of a heart failure subject's withdrawal including but not limited to 1) whether the withdrawal of the heart failure

subject resulted from a decision by the subject or by the investigator and the reason(s) for the withdrawal, if known. The clinical investigator should also document whether the withdrawal was from all components of the research study or would allow follow-up for clinical outcomes at Month 24. See the Manual of Procedures (MOP) for further details.

Known events/outcomes collected for REVIVAL up to the time of termination should be reported on the study eCRFs. See the MOP for further details.

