8.3.3 Modeling of Clinical Outcomes

We seek to estimate the morbidity and mortality rates in this population and to evaluate the effectiveness of baseline factors in determining their prognosis. To accomplish this goal [objective 1], we will use logistic regression for dichotomous outcomes (e.g., proportion of subjects with an interest in VAD therapy), Poisson regression for count outcomes (e.g., number of hospitalizations per participant), Cox proportional hazard models for time-to-event outcomes (e.g., survival, time to VAD implantation) and linear mixed-effects models for continuous outcomes (e.g., quality of life, functional capacity)^[30-32]. For time-to-event outcomes, survival time will be defined as the time from consent to the event or, for participants who did not experience an event, to the last study visit. Given the potentially small number of events, differences between groups will be tested by means of the log rank test. For longitudinal continuous outcomes, we will model correlated errors with a first order autoregressive (AR1) process since it is reasonable to assume adjacent values are more correlated than observations father apart in time. Alternative variance-covariance structures will be investigated, if needed.

Univariable models will be developed first, using baseline characteristics as the predictors. Multivariable models will be built incorporating known prognostic factors (i.e., those identified in the literature) and those suggested from the univariable analyses (i.e., those with p<0.10). Given the sample size and the potential for small numbers of events (in time-to-event outcomes), we will apply the principle of parsimony to the number of potential prognostic factors included in the ultimate model. In addition to using such standard methods to develop multivariable risk prediction models, we will derive simplified scoring systems to aid in clinical decision-making. Alternative classification schemes (e.g., CART) will be employed as sensitivity analyses. To assess the performance of the risk prediction models, we will evaluate their calibration (or reliability) discrimination and accuracy^[33].

Comparison among existing classification systems and the use of second early assessments (baseline B measures instead of baseline A measures) with the improved risk prediction model(s) developed above will be based on the concordance index, parsimony of the model, and the other performance metrics described above^[34].

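### Section 8.3.3 censors event-free subjects at their last visit but counts off-visit events at their own date, which biases 2-year risk modestly upward

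*Protocol*

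**What the plan says.** Protocol section 8.3.3 gives two end dates. For a subject with an event, "survival time will be defined as the time from consent to the event". The alternative is, "for participants who did not experience an event, to the last study visit". The first date is not tied to a visit; the second is.

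Event capture is wider than the visit schedule:

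- Section 4.11, on study-procedure adverse events and outcomes: "These will be recorded using data available in the medical chart as well as information gathered on patient diaries". It adds: "Adverse event and outcomes data will be collected at all visits following the baseline A visit and in cases of early subject termination".
- Section 5.3: "Known events/outcomes collected for REVIVAL up to the time of termination should be reported on the study eCRFs". The investigator also documents whether a withdrawing subject "would allow follow-up for clinical outcomes at Month 24".
- Section 3.2 ends follow-up at death, transplant or durable VAD, and "events/outcomes up through the point of the outcome will be reported on the eCRFs".

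The visits are listed in section 3.4: "Clinic visits: Baseline A, Baseline B and follow up visits at 6,12,18 and 24 months". With Baseline B at two months, gaps between visits reach six months. No section limits counted events to those on or before the last visit, and none credits event-free subjects with time up to their last known status.

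**The concern.** Kaplan-Meier and Cox methods require that the censoring date does not depend on the outcome. Here it does. Take a subject who stops visits after month 6 and allows outcome follow-up. If found to have died at month 20, the subject contributes 20 months and an event. If found alive at Month 24, the subject contributes 6 months, and 18 months of known survival are discarded. The numerator is kept and part of the denominator is lost.

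A second route needs no drop-out. In an analysis of death alone, a VAD or transplant recipient has no later study visit. Read literally, the clause censors that subject at the visit before the procedure, up to six months too early, although survival to the procedure is documented. A subject who dies in the same interval keeps the whole interval.

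Section 8.3.3 sets out to estimate morbidity and mortality rates and to build risk scores whose calibration will be judged, so the level of absolute risk matters.

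**Working it through.** **1. The plan's own figures.** Section 8.2 expects 30% of 400 subjects to have a clinical outcome or drop out: 400 × (1 − 0.30) = 280. The half-width is 1.96 × √(p(1−p)/280), which gives 2.55% at p = 5% and 5.86% at p = 50%. The stated 2.6% and 5.9% reproduce. At p = 20% it is 4.7%.

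**2. Assumptions.** The protocol does not split the 30% into events and drop-out, nor say how many who stop visits will have later outcomes known. Both are varied. Event times and stopping times are exponential and independent; visits are at 0, 2, 6, 12, 18 and 24 months; each scenario has 1,000,000 simulated subjects. The combined share is 1 − (1 − risk)(1 − drop-out), for example 1 − 0.80 × 0.90 = 28%.

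**3. 24-month Kaplan-Meier risk under the section 8.3.3 rule,** by how long outcomes remain known after a subject stops visits:

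| True risk / drop-out | Combined | To Month 24 | Until next visit window closes | Until date of stopping | Nothing after last visit |
|---|---|---|---|---|---|
| 25% / 5% | 28.8% | 25.7% (+0.7) | 25.3% (+0.3) | 25.1% (+0.1) | 25.1% |
| 20% / 10% | 28.0% | 21.2% (+1.2) | 20.5% (+0.5) | 20.1% (+0.1) | 20.0% |
| 15% / 15% | 27.8% | 16.4% (+1.4) | 15.6% (+0.6) | 15.2% (+0.2) | 14.9% |
| 10% / 20% | 28.0% | 11.3% (+1.3) | 10.6% (+0.6) | 10.2% (+0.2) | 10.0% |

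Departures of 0.1 point in the last column are simulation noise. Censoring at the last date on which status is known returns the true risk to within 0.1 point in every cell.

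In the Month 24 column, 2.7, 5.5, 8.6 and 11.9% of person-time is lost. In the 20% / 10% row the event rate is 11.85 per 100 person-years against a true −ln(0.80)/2 = 11.16, a ratio of 1.06. Across the four rows the rate is about 3 to 13% too high.

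**4. A scenario beyond the planning figure.** With event risk alone at 30% and 10% per year stopping visits, the combined share is 1 − 0.70 × 0.90² = 43%. The rule gives 33.0% if all who stop have outcomes known to Month 24, 31.7 to 31.9% if half do, and about 30.5% if none do.

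**5. Mortality-only analysis, no drop-out.** Assume 2-year mortality of 15 to 25% and VAD or transplant in 10 to 30%. Censoring recipients at the visit before the procedure raises Kaplan-Meier mortality by 0.2 points (15% mortality, 10% procedures) to 0.9 points (25%, 30%). Between 1.1 and 3.8% of person-time is lost. Censoring at the procedure date removes the excess.

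**6. Does a last-known-status date suffice on its own?** Not if events are easier to find than survival. Take the setting of step 4, with events found to Month 24 in everyone but event-free status confirmed in only half of those who stop. Censoring at the last known event-free date then still gives about 31.0 to 31.5%, depending on whether the unconfirmed half are censored at stopping or at their last visit. Counting events only up to the date through which event-free status would also have been established gives 30.0%.

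**The case against.** The strongest reply is that the effect is small and limited to a minority. Subjects who attend Month 24, projected at 70%, lose essentially no time. Section 5.3 does not promise Month 24 outcomes for everyone who withdraws; it asks that permission be documented and that known events be reported up to termination. For a subject who refuses further follow-up, events and person-time stop close together. For the composite in Objective 1 that counts MCSD and transplant as events, those events carry their own dates, so the second route does not arise. The study is an observational, hypothesis-generating registry. Section 8.1 plans selection and pattern-mixture sensitivity analyses, and section 8.1 leaves further detail to the SAP, which was not available here.

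Most of this stands and sets the size. It does not remove the point. The censoring rule is stated, not left open, and following it gives a biased estimate. The planned sensitivity analyses address outcomes that were not observed; they do not restore known event-free time that the definition discards.

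Three stronger readings are tempting and are not supported:

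- *A bias of 3 points or more.* This needs event risk alone at 30%, 10% per year stopping, and outcomes known to Month 24 in all who stop. The combined 43% exceeds the 30% in section 8.2. Such risk is not implausible, since section 4.3 cites about 60% 2-year event-free survival at peak VO₂ 10–14 ml/min/kg in an older cohort, but it is not what this protocol plans for.
- *All survivors lose person-time.* Only those who stop visits or miss the last one do.
- *Hazard ratios are distorted.* This could happen for factors linked to missed visits, but no calculation here includes a covariate.

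**Conclusion.** The clause is wrong as written; severity is moderate. Within the planned 30% for events plus drop-out, 2-year risk is overstated by about 0.1 to 1.4 points: 0.7 to 1.4 if outcomes are known to Month 24 for all who stop, 0.3 to 0.6 if known until the next visit window closes, 0.1 to 0.2 if known only until stopping, and nil if nothing is known after the last visit. The mortality-only route adds about 0.2 to 0.9 points under the assumed rates.

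These excesses are below the sampling half-width (4.7 points at 20%, n = 280), but they run in one direction and do not shrink with more subjects. The figures rest on an assumed split of events and drop-out, exponential times, and stopping that is independent of the event. The direction of the bias follows from the text once off-visit events are counted; the size depends on these assumptions.

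**What to change.** Replace the censoring clause in section 8.3.3 with: *to the earliest of 24 months and the date last known free of the event from any source (visit, contact, chart review, Month 24 outcome check); in mortality-only analyses, VAD and transplant recipients are censored at the procedure date.*

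Add one rule for any subject who stops visits: *events count only up to the date through which event-free status would also have been established, that is, Month 24 if outcome follow-up is allowed and completed, otherwise the date of stopping or last contact.* This second sentence is needed because the first does not protect against events being found more readily than survival (step 6 of the working).

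The cost is two sentences and a little more data work to record or derive a last-known-status date. The eCRFs are not shown, so whether that needs a new field cannot be judged. No visit, sample size or model changes.

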6.2 Study Procedures and Assessments

6.2.1 Baseline A

Initiation of baseline A will occur with the heart failure subject signing the Informed Consent document(s). Standard of Care (SOC) testing will be included in the heart failure subject evaluation for this visit. All SOC procedures are labeled as such below. All other procedures will be research expenses. After signing the informed consent document(s), subjects will undergo the following testing and evaluation:

- 1. Directed history and physical (including NYHA and INTERMACS Patient Profile)
- 2. ECG (SOC)
- 3. Blood draw for:
 - a. CBC with platelets and differential count [SOC]
 - b. Comprehensive metabolic panel [SOC]
 - c. Uric Acid
 - d. Total cholesterol
 - e. INR
- 4. Handgrip strength (by dynamometer)
- 5. Gait Speed Test
- 6. 6 minute walk test
- 7. Quality of life and health utility questionnaires
- 8. Patient preference questionnaire
- 9. Caregiver participation overview with heart failure subject
- 10. Dispense patient diary

If the heart failure subject has an historic ECG on file that was completed within 30 days of the assessment date, this may be used for fulfillment of this visit requirement if, in the opinion of the investigator, the historic ECG is highly likely to represent the subject's current health status.

If the heart failure subject has historic laboratory results on file that were drawn within 14 days of the assessment date, these results may be used for fulfillment of this visit requirement if, in the opinion of the investigator, the historic laboratory result(s) are highly likely to represent the subject's current health status.

Baseline A procedures should be completed within two weeks of consent. The baseline B visit should be scheduled to occur two (2) months (\pm 30 days) after consent.

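### AR(1) errors are the default for visits at 0, 2, 6, 12, 18 and 24 months, but the correlation is not tied to elapsed time

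*Protocol*

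**What the plan says.** Protocol Section 8.3.3 assigns "linear mixed-effects models for continuous outcomes (e.g., quality of life, functional capacity") and then fixes the error structure: "correlated errors with a first order autoregressive (AR1) process". The reason given is that "it is reasonable to assume adjacent values are more correlated than observations father apart in time". The fallback is one sentence without a criterion: "Alternative variance-covariance structures will be investigated, if needed". Random effects are not specified.

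The schedule is in Section 3.4 ("Clinic visits: Baseline A, Baseline B and follow up visits at 6,12,18 and 24 months") and Section 6.2.1 ("The baseline B visit should be scheduled to occur two (2) months", within 30 days either way). Sections 6.2.3 to 6.2.6 allow ±45 days at months 6, 12 and 18, and ±30 days at month 24. Walk distance (Section 4.2) and quality of life (Section 4.14) are collected at all six visits. Section 8.4 carries the general approach of Section 8.3 over to caregiver burden, which Objective 3 schedules at baseline B and at 6, 12, 18 and 24 months.

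**The concern.** A first-order autoregressive process, as usually defined and as most software fits it by default, depends on the order of the visits. Every adjacent pair gets the same correlation ρ, every pair two visits apart gets ρ², and so on. Here the adjacent visits are nominally 2, 4, 6, 6 and 6 months apart. A single ρ must therefore serve both a 2-month gap and a 6-month gap, although the reason given for the choice concerns distance in time.

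This would affect the standard errors and confidence intervals of the longitudinal models. Describing functional capacity and quality of life over two years is part of Objective 1, and this is the model named for those outcomes. Intervals would tend to be too wide across the short early gap and too narrow across the 6-month gaps. The unequal spacing is known now and need not be discovered from the data.

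**Working it through.** **The plan's own figure.** The protocol gives no figure that depends on this covariance. Its only computed design figure, the precision in Section 8.2, reproduces: 1.96·√(0.05·0.95/280) = 2.55% and 1.96·√(0.5·0.5/280) = 5.86%, stated as 2.6% and 5.9%. It has no bearing on this point.

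**Nominal gaps by number of visits apart (lag).**

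| Lag | Gaps in months | Visit-order AR(1) correlation |
|---|---|---|
| 1 | 2, 4, 6, 6, 6 | ρ |
| 2 | 6, 10, 12, 12 | ρ² |
| 3 | 12, 16, 18 | ρ³ |
| 4 | 18, 22 | ρ⁴ |
| 5 | 24 | ρ⁵ |

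Gaps of 6, 12 and 18 months each appear at two lags, so equal distances in time get unequal correlations.

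**Effect of the windows.** Suppose month 6 is seen 45 days early (4.5 months) and month 12 is seen 45 days late (13.5 months), both within protocol. Baseline A and month 6 are then 4.5 months apart and get ρ². Months 6 and 12 are 13.5 − 4.5 = 9 months apart and get the larger ρ.

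**Size of the standard-error error.**
- Assumed truth: correlation r^(gap/6), with r the correlation at 6 months. The main range is r = 0.5 to 0.8; this is an assumption, as the protocol gives no value.
- Fitted model: the visit-order AR(1) that maximises the large-sample likelihood under that truth, with a separate mean per visit and complete data.
- Result: model-based SE divided by true SE. For a change between two visits with the variance fitted at about its true value, this is √[(1 − fitted correlation)/(1 − true correlation)].

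Worked case, r = 0.7, with fitted ρ = 0.755:
- A to B: true correlation 0.7^(2/6) = 0.888; √(0.245/0.112) = 1.48.
- B to month 6: true correlation 0.7^(4/6) = 0.788; √(0.245/0.212) = 1.08.
- Month 6 to 12: true correlation 0.7; √(0.245/0.300) = 0.90.

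The measurement-error runs replace the true correlation by (1 − e)·r^(gap/6), with e = 0.1 to 0.3 and r = 0.5, 0.7 and 0.8. Worked case, r = 0.8 and e = 0.3, with fitted ρ = 0.587: A to B has true correlation 0.7·0.928 = 0.650, so √(0.413/0.350) = 1.09; a 6-month gap has 0.7·0.8 = 0.56, so √(0.413/0.44) = 0.97.

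| Contrast | No measurement error, r 0.5–0.8 | 10–30% measurement error |
|---|---|---|
| A to B | 1.42–1.50 | 1.09–1.29 |
| B to month 6 | 1.06–1.08 | 1.02–1.05 |
| Month 6 to 12 | 0.90–0.91 | 0.93–0.97 |
| A to month 24 | 1.00 | 1.01–1.14 |
| Linear slope | 0.94–0.96 | 0.98–1.15 |

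**Does a random intercept cure it?** No. With a random intercept holding 0, 30% or 50% of the variance, both in the truth and in the fitted model, the A-to-B ratio is still 1.42 at r = 0.5 and 1.48 at r = 0.7, and the 6-month-gap ratio is 0.91 and 0.90.

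**The case against.** The strongest reply is that the protocol never says the process runs by visit order. Its justification speaks of time, so a continuous-time AR(1) is a possible reading, and Section 8.1 defers detail to the statistical analysis plan. That stands as far as it goes. But the protocol does name a structure whose usual meaning is the visit-order one, so the wording needs settling. If continuous time is meant, a short phrase suffices.

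A reader might infer that AR(1) contradicts the plan's own rationale. At nominal times it does not: in the lag table, no pair closer in time gets a lower correlation than a pair farther apart. The fault is unequal correlations for equal gaps, and only the visit windows can reverse the order.

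A reader might also infer that the two-month reassessment in Objective 1 is compromised, since the A-to-B change usually shows the largest distortion. The documents do not support this. Section 8.3.3 compares baseline B with baseline A through the concordance index and other performance measures of risk models, which this error structure does not enter. No test of mean A-to-B change is named. For that contrast the error is also conservative, and it is not always the largest: at r = 0.8 with 30% measurement error, A to B is 1.09 and the slope is 1.15.

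Finally, Section 8.1 promises checks of model assumptions and Section 8.3.3 allows other covariance structures. These reduce the risk. Without a criterion, they do not replace a default that can be seen beforehand to fit the schedule poorly. The registry is observational, sized on logistics and largely descriptive, which limits the consequence.

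**Conclusion.** The point holds as a modest defect of specification: a default AR(1) is fixed for unequally spaced visits without being tied to elapsed time. If it is fitted in its usual visit-order form and correlation decays at 0.5 to 0.8 per 6 months, standard errors are about 3–10% too small for 6-month-gap changes and about 9–50% too large for the A-to-B change. The slope standard error lies between about 6% too small and 15% too large.

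These ranges rest on an assumed correlation, on 0 to 30% measurement-error variance, on complete data at nominal times, and on the fallback structures not being used. The understatement for 6-month gaps appeared in every scenario run; the direction for the slope did not stay constant. The models affected are those for quality-of-life and functional-capacity trajectories and, through Section 8.4, caregiver burden, where the gaps are 4, 6, 6 and 6 months; the caregiver case was not computed separately.

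**What to change.** In Section 8.3.3, replace the AR(1) wording with a continuous-time AR(1) (spatial power) structure, in which correlation is a function of actual days from consent. Add a subject random intercept where it can be estimated, and name an unstructured covariance over the six nominal visits as the check. Under the decay assumed above without measurement error, the continuous-time form brings the standard-error ratio to 1.00 by construction; the unstructured check is there to show departures from that form, including measurement error.

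No new data or visits are needed, since visit dates are available. The change is one model option with the same number of correlation parameters as AR(1), plus one variance parameter if the random intercept is not already in the mixed model.
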